8.2 SAFETY ASSESSMENTS

The CREDOenAP program intervention is considered a low-risk intervention due to its behavioral nature. It does not involve the use of any drugs or invasive procedures. However, several measures have been planned to assess and ensure the safety of participants in the intervention:

- Adverse event monitoring: During the scheduled follow-up sessions within the intervention, the professional responsible for conducting the sessions will also be in charge of identifying and reporting any adverse events. Any signs of physical or emotional discomfort or change will be recorded. Subsequently, the event will be evaluated to determine its severity and the appropriate response protocol.

In the event of an adverse event, it will be assessed to determine its severity and whether it requires additional medical attention or poses a risk to the participant's safety. If necessary, the participant will be referred to receive specific treatment. Finally, their continuation in the intervention will be evaluated.

All identified adverse events will be documented in the study's official registry.

8.3 ADVERSE EVENTS AND SERIOUS ADVERSE EVENTS

8.3.1 DEFINITION OF ADVERSE EVENTS

This protocol uses the definition of Adverse Event established in 21 CFR 312.32(a):

"Any unintended medical occurrence in a clinical study participant, associated with the use of the investigational intervention, regardless of whether it is causally related to it."

In this specific case, the Adverse Events that may be observed include:

- Physical symptoms.
- Hypoglycemia/Hyperglycemia.
- Physical discomfort.
- Metabolic disturbances.

Although this study is not expected to have a high incidence of Adverse Events due to its nature, any notable event will be documented and evaluated by the research team.

8.3.2 DEFINITION OF SERIOUS ADVERSE EVENTS

In this protocol, a Serious Adverse Event (SAE) is defined as any occurrence that involves:

- Patient death.
- Risk to the patient's health or physical integrity.
- Hospitalization.
- Any other medical event resulting from the intervention.

Given the nature of the intervention, the occurrence of Serious Adverse Events is not expected during the course of the study.

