2.3 RISK/BENEFIT ASSESSMENT

2.3.1 KNOWN POTENTIAL RISKS

Due to the nature of the study, which focuses on dietary and lifestyle changes in patients, the risks associated with this type of intervention are very low. However, potential risks may include:

- **Immediate risks:** Dietary changes and increased physical activity may trigger mild adverse effects. For example, participants may experience episodes of constipation, fatigue, or minor muscle discomfort related to increased physical activity.
- **Long-term risks:** In individuals with type 2 diabetes (T2DM) who discontinue pharmacological treatment due to metabolic improvement, there is a risk of hyperglycemia if the long term adherence to lifestyle programm fails. This risk will be minimized through close medical monitoring during the study.

No alternative interventions were proposed due to the low risk of adverse effects and to avoid interfering with the intervention as defined in the protocol.

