The randomization sequence will be generated by an independent statistician.

The intervention has been designed to last 6 months. During this period, participants in the intervention group will receive individualized follow-up, both in-person and via telephone, aimed at achieving lifestyle changes (dietary modifications, increased physical activity, improved emotional management, etc.).

The control group will receive standard care for T2DM, with follow-up according to routine primary care practices. They will participate in periodic assessments but will not receive any components of the intervention program.

The study design includes a follow-up assessment 12 months after the end of the intervention (18 months from the start of the intervention) to evaluate the sustainability and long-term effects of the intervention.

Finally, no interim analyses or additional sub-studies are planned within this protocol.

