10.1.6 SAFETY OVERSIGHT

Due to the non-pharmacological nature of the intervention, it is considered low risk for participants. Therefore, safety oversight will be managed by the research team, who will be responsible for identifying and reporting any adverse events that occur. The internal safety monitoring plan outlined in this protocol consists of periodic meetings of the research team, during which any incidents arising from the intervention will be discussed, and adherence to the defined protocol and Good Clinical Practice will be evaluated.

Any adverse event identified will be recorded and reported to the participant, the Principal Investigator, and Parc Sanitari Pere i Virgili. In the case of repeated serious adverse events, the situation will be urgently assessed, and if necessary, the intervention may be considered for temporary suspension.

The creation of an independent Data Safety Monitoring Board (DSMB) is not planned, as the type of intervention and the risk profile of the study do not require it.

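### The fourth item of the SAE definition in 8.3.2 makes attribution to the intervention enough for an event to be serious, so it takes in anticipated mild effects and can be met only in Group A

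*Protocol*

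**What the plan says.** Protocol 8.3.2 states that "a Serious Adverse Event (SAE) is defined as any occurrence that involves" one of four things: the patient's death, a risk to health or physical integrity, hospitalization, or, as the last item, "Any other medical event resulting from the intervention". The same section then says that "the occurrence of Serious Adverse Events is not expected during the course of the study".

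Section 2.3.1, on known risks, says that "Dietary changes and increased physical activity may trigger mild adverse effects" and gives examples: "participants may experience episodes of constipation, fatigue, or minor muscle discomfort related to increased physical activity".

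The safety sections that follow treat mild events and SAEs as different classes:
- **8.3.4** collects mild events for 7 days after study completion and SAEs for 30 days. It gives classification of the type of event to a clinician outside the intervention.
- **8.3.5** allows up to 5 days to assess an adverse event. **8.3.6** is a separate SAE pathway that contains a 24-hour referral.
- **8.3.3.1** grades severity and notes that a severe event need not be a serious one. **8.3.3.2** assesses relatedness as its own step.
- **10.1.6** attaches a consequence to the SAE label: "In the case of repeated serious adverse events, the situation will be urgently assessed", after which a temporary suspension may be considered.

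On the control group, section 4.1 says: "They will participate in periodic assessments but will not receive any components of the intervention program".

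**The concern.** Seriousness is normally a property of what happened to the patient, and causality is a separate judgement. The fourth item merges the two. Any medical event counts as serious once it is put down to the program, however slight it is. The definition then takes in effects that the protocol itself calls mild and expects to see, and it classes the same event differently according to arm.

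What is at stake is the meaning of the SAE label. If staff follow the wording, trivial events enter the SAE record and the review of repeated SAEs. If they ignore it, they decide what is serious by an unwritten rule, in an open-label trial with no DSMB (10.1.6) and no independent external monitoring (10.1.7). In neither case does an SAE count describe the two arms on the same terms.

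**Working it through.** The point concerns the wording of a definition, so no calculation applies. The check sets the sections side by side.

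1. **How the items combine.** The definition covers an occurrence involving any item on the list. The items cannot all be required together, since every SAE would then have to be a death. Meeting one item is enough.

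2. **Whether anything narrows the fourth item.** It carries no qualifier of its own. Section 8.3.3.1 defines mild, moderate and severe but does not say what is serious. Section 8.3.3.2 deals with relatedness, 8.3.3.3 with expectedness, and 8.3.8 adds no further events. No other section limits the item.

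3. **Applying it to the anticipated effects.** Constipation, fatigue or muscle discomfort brought on by the diet or exercise program is a medical event that results from the intervention. It meets the fourth item as written.

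4. **Consistency with the rest of the protocol.**

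| Section | What it implies | Conflict with the fourth item |
|---|---|---|
| 8.3.2, closing sentence | No SAEs are foreseen | The item captures effects foreseen in 2.3.1 |
| 8.3.4 | Mild events 7 days, SAEs 30 days | A mild event attributed to the program falls under both windows |
| 8.3.5 and 8.3.6 | Separate AE and SAE pathways | The same mild event belongs to both |
| 8.3.3.1 and 8.3.3.2 | Severity and relatedness are separate judgements | Relatedness alone settles seriousness |

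5. **The same event in each arm.** Take mild fatigue after increased walking.
   - Group A, attributed to the program: the fourth item is met, so it is an SAE.
   - Group B: the participant receives no program component (4.1), so the fourth item cannot be met. The event is an SAE only if one of the first three items applies.

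   Those three items are open to both arms, so the asymmetry belongs to the fourth item alone.

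6. **How easily attribution is reached.** Under 8.3.3.2 a temporal relationship is sufficient to call an event related to study procedures, which include the intervention. If that judgement is used to decide whether an event results from the intervention, the threshold is low.

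7. **Size.** The protocol gives no rate for mild effects. Section 8.3.1 says only that a high incidence of adverse events is not expected. No count of misclassified events can be derived.

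**The case against.** The best reply is that this is loose drafting which no one would apply literally. The item closes a list of grave outcomes, and the surrounding sections plainly separate mild from serious events, so a comparable event was probably meant. An external clinician classifies events under 8.3.4, which makes automatic escalation of mild complaints less likely. This is a fair account of the probable intent, but it does not cure the text. The word that would limit the item is absent, and the second item (risk to health) is too broad to supply the limit by context. The external clinician has no written definition of seriousness to apply other than 8.3.2.

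The reply is right against several stronger readings that a reader might infer:
- **Mild effects would automatically trigger a 24-hour referral and suspension.** In 8.3.6 the 24-hour sentence follows directly on the provision for severe urgency and can be read as covering only those cases. In 10.1.6 suspension is discretionary and has no count threshold.
- **A between-arm safety comparison would be biased.** None is planned: section 9.4.4 gives safety analyses as not applicable, and SAE frequency is not an endpoint in section 3.
- **True serious events would be lost among trivial ones.** Symptoms, onset, duration and treatment are recorded for each event (8.3.4), and safety outcomes are listed by participant (9.4.8). Deaths and hospitalizations should remain identifiable.
- **A number of spurious SAEs can be forecast.** Any such figure would rest on an incidence that the protocol does not give.

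**Conclusion.** The point holds as a defect of definition. As written, the fourth item makes attribution to the intervention sufficient for seriousness, contradicts 8.3.2's own expectation and the division between mild and serious events in 8.3.4 to 8.3.6, and can be met in one arm only. This rests on the literal wording and on the effects named in 2.3.1 being attributed to the program when they occur.

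The consequences are limited to how events are classified and reported and to what feeds the review of repeated SAEs in 10.1.6. The endpoints, the sample size and the planned analyses are untouched. The extent of misclassification cannot be quantified from the protocol. The correction is worth making because the rule is wrong as stated and costs almost nothing to put right.

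**What to change.** In 8.3.2, either delete the fourth item or restrict it to other medically important events comparable in seriousness to those already listed. State that seriousness is judged regardless of cause and by the same rule in Groups A and B. Name the external clinician who classifies events under 8.3.4 as the person who applies it; the clinician in 8.3.3.3 is assigned expectedness only. Record relatedness separately under 8.3.3.2.

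Then reconcile 8.3.2 with 2.3.1, 8.3.4 to 8.3.6 and 10.1.6, so that an event graded mild and anticipated does not fall under two reporting pathways.

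The cost is about one line of wording and a consistency check of those sections, with no added data collection and no change to the sample size or analyses.

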8.3.3 CLASSIFICATION OF AN ADVERSE EVENT

8.3.3.1 SEVERITY OF EVENT

For adverse events (AEs) not included in the grading system defined in the protocol, the following guidelines will be used to describe severity:

- **Mild:** Events require minimal or no treatment and do not interfere with the participant's daily activities.
- **Moderate:** Events result in a low level of inconvenience or concern with therapeutic measures. Moderate events may cause some interference with functioning.
- **Severe:** Events disrupt the participant's usual daily activities and may require systemic pharmacological treatment or other interventions. Severe events are often potentially life-threatening or disabling. It should be noted that the term "severe" does not necessarily equate to "serious."

8.3.3.2 RELATIONSHIP TO STUDY INTERVENTION/EXPERIMENTAL MANIPULATION

All adverse events (AEs) will have their relationship to study procedures, including the intervention, assessed by a qualified clinical professional, based on temporal association and clinical judgment. The degree of certainty regarding causality will be classified using the following categories:

- **Related** – The AE is known to occur with study procedures, there is a reasonable possibility that the study procedures caused the AE, or there is a temporal relationship between the study procedures and the event. "Reasonable possibility" means there is evidence suggesting a causal relationship between the study procedures and the AE.
- **Not Related** – There is no reasonable possibility that the study procedures caused the event, there is no temporal relationship between the study procedures and the onset of the event, or an alternative etiology has been established.

8.3.3.3 EXPECTEDNESS

A clinical professional with appropriate experience in type 2 diabetes (T2DM) from the Endocrinology Department of Hospital de Mar, Barcelona, and external to the intervention, will be responsible for determining whether an adverse event (AE) is expected or unexpected. An AE will be considered unexpected if the nature, severity, or frequency of the event is not consistent with the previously described risk information for the study procedures.

8.3.4 TIME PERIOD AND FREQUENCY FOR EVENT ASSESSMENT AND FOLLOW-UP

All procedures and events occurring in the patients will be recorded. These records will be made every 15 days, coinciding with the scheduled follow-up visits of the intervention. The classification of the type of event will be carried out by a clinician external to the intervention, who can independently assess the severity of the event.

All adverse events occurring at any time after obtaining informed consent will be recorded, up to 7 days after the study completion for mild adverse events, or up to 30 days for serious adverse events. At each study visit, the investigator will inquire about the occurrence of adverse or serious adverse events since the last visit. Events will be followed up to obtain information on outcomes until resolution or stabilization.

For each identified event, the symptoms, onset date, duration of symptoms (if applicable), and any required treatment will be documented. Any deterioration or change in the patient's baseline conditions, both related to T2DM and other comorbidities, will also be recorded as an adverse event.

8.3.5 ADVERSE EVENT REPORTING

All information related to an adverse event will be recorded both in the patient's shared medical record and in the study's official registry.

The person responsible for recording will be the investigator conducting the follow-up calls or the professional performing the examinations scheduled in the protocol.

Once an adverse event has been identified, it will be reported to the principal investigator of the intervention to assess the feasibility of the patient continuing in the study. In addition, the patient's primary care physician will be contacted to evaluate the necessary treatment. This assessment will be carried out within a maximum of 5 days.

8.3.6 SERIOUS ADVERSE EVENT REPORTING

Serious adverse events (SAEs) will be recorded both in the patient's shared medical record and in the study's official registry. The person responsible for recording will be the investigator

conducting the follow-up calls or the professional performing the examinations scheduled in the protocol.

Once a serious adverse event has been identified, it will be reported to the principal investigator of the intervention, who will assess the feasibility of the patient continuing in the study.

Additionally, the patient's primary care physician will be contacted to evaluate the patient's health status and determine the appropriate treatment. In cases of severe urgency, an emergency physician will be contacted. This referral will be made within 24 hours of reporting the event.

8.3.7 REPORTING EVENTS TO PARTICIPANTS

All adverse events and unexpected findings regarding the patients' health status will be communicated. This information will be conveyed privately and individually to each patient, either via telephone contact or during the scheduled follow-up visits with their primary care physician.

8.3.8 EVENTS OF SPECIAL INTEREST

No events of special interest, other than those previously described in the protocol, have been identified.

8.3.9 REPORTING OF PREGNANCY

In the event that a pregnancy is identified in any participant, the situation will be appropriately communicated to the patient. Subsequently, the participant's health status will be documented in the study's official registry. As previously indicated, pregnancy constitutes an exclusion criterion in this study, and participation in the intervention will be immediately discontinued.

8.4 UNANTICIPATED PROBLEMS

8.4.1 DEFINITION OF UNANTICIPATED PROBLEMS

This protocol uses the definition of Unanticipated Problems as established by the Office for Human Research Protections (OHRP). The OHRP considers unanticipated problems involving risks to participants or others to generally include any incident, experience, or outcome that meets all of the following criteria:

- Unexpected in terms of its nature, severity, or frequency, taking into account:
 - (a) the study procedures described in protocol-related documents, such as the protocol approved by the Research Ethics Committee and the informed consent document; and
 - (b) the characteristics of the participant population being studied;
- Related or possibly related to participation in the research (where "possibly related" means there is a reasonable possibility that the incident, experience, or outcome was caused by

the study procedures); and suggests that the research places participants or others at a greater risk of harm (including physical, psychological, economic, or social harm) than previously known or recognized.

8.4.2 UNANTICIPATED PROBLEMS REPORTING

The principal investigator will be responsible for reporting any unanticipated problem to the responsible entity, Parc Sanitari Pere i Virgili. The report of the problem will include:

- Study identification information
- Detailed description of the incident
- Justification for why it is considered an unanticipated problem
- Description of the proposed protocol changes or corrective measures adopted in response

The deadlines for reporting incidents are as follows:

- Unanticipated problems that constitute serious adverse events (SAEs) will be reported to Parc Sanitari Pere i Virgili within a maximum of 10 days from the investigator becoming aware of the event.
- Any other unanticipated problem will be reported within no more than 15 days.

8.4.3 REPORTING UNANTICIPATED PROBLEMS TO PARTICIPANTS

Patients will be informed if an unanticipated problem occurs and poses any risk to them. They will be notified individually if the unanticipated problem affects a specific patient; otherwise, they will be informed collectively if the problem affects the entire group. Notification will be made via telephone contact, by letter, or, if necessary, through a meeting with all participants in the intervention.

9 STATISTICAL CONSIDERATIONS

9.1 STATISTICAL HYPOTHESES

Primary Endpoint:

The primary hypothesis is based on the null hypothesis (H_0), which states that there is no difference in the percentage of type 2 diabetes (T2DM) remission between the intervention group and the control group. Conversely, the alternative hypothesis (H_1) states that the percentage of T2DM remission will be significantly higher in the intervention group compared to the control group. An efficacy analysis is planned and will be evaluated right after the end of the intervention.

Secondary Endpoints:

The null hypothesis (H_0) states that there will be no significant differences in the proposed secondary variables (metabolic, behavioral, and quality-of-life variables) between the intervention group and the control group. Conversely, the alternative hypothesis (H_1) states that there will be statistically significant differences in the proposed secondary variables (metabolic, behavioral, and quality-of-life variables), with more favorable outcomes for the intervention group compared to the control group. An efficacy analysis of the intervention is planned, and the evaluation will be carried out 12 months after the end of the intervention.

9.2 SAMPLE SIZE DETERMINATION

Based on the primary variable of the intervention, the percentage of T2DM remission, the required sample size has been calculated to observe statistically significant differences. This variable will be coded dichotomously. A total of 120 volunteers (60 per arm) will be recruited for the study. Accepting an alpha risk of 0.05 (5%) and a beta risk of less than 0.2 in a two-sided test, at least 52 subjects in the control group and 52 subjects in the intervention group would be required to detect as statistically significant a 20% difference between two proportions (primary endpoint: T2DM remission). For the control group, the expected remission rate ranges from 0 to 5%, whereas in the intervention group, it is expected to be at least 25%. The remission rates have been benchmarked against previous studies (Lean et al., n.d.). An estimated loss to follow-up rate of 15% has been considered.

Given the estimated 15% loss to follow-up, the sample size has been increased to 60 participants instead of 52. This ensures that the statistical power of the analysis will be preserved.

9.3 POPULATIONS FOR ANALYSES

The populations identified to be included in the study are as follows:

Intention-to-Treat (ITT) Analysis: All randomized participants who have completed the minimum required follow-up and for whom clinical data and questionnaires are available at baseline (T0), 6 months post-intervention (T-6 months), and 18 months post-intervention (T-18 months).

Per-Protocol Analysis: Participants who have completed at least the main intervention session and for whom clinical data and questionnaires are available at a minimum of baseline (T0) and 6 months post-intervention (T-6 months).

Sensitivity Analysis: Sensitivity analyses will be performed in subgroups according to participant characteristics, including population with more than five years since T2DM diagnosis, sex, and age.

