6.4 STUDY INTERVENTION/EXPERIMENTAL MANIPULATION ADHERENCE

To monitor and promote participant adherence to the intervention activities, biweekly telephone contacts will be conducted. During these contacts, the following will be performed:

- 24-hour dietary recall survey: using photographs of the participant's food intake over one day, their diet will be recorded.
- Overall health check of the participant.
- Review and adjustment of daily exercise plan.

A participant will be considered adherent to the intervention if they complete the initial session and at least 70% of the follow-up sessions. All adherence information will be recorded in the official intervention log.

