9.4.2 ANALYSIS OF THE PRIMARY ENDPOINT(S)

The primary endpoint is the change in glycated hemoglobin (HbA1c, %) from baseline to 6 months. HbA1c is measured as a continuous variable on an interval scale. The endpoint will be calculated as the absolute difference between baseline HbA1c and the value obtained at 6 months.

The primary analysis will be performed using analysis of covariance (ANCOVA) with treatment group (intervention vs. control) as the fixed factor, and baseline HbA1c as a covariate to improve precision. Additional prespecified covariates will include age, sex, study site, and randomization block, based on their potential clinical relevance and to ensure adjustment for any residual imbalance despite randomization. A secondary, confirmatory analysis will be conducted using a

mixed-effects model for repeated measures (MMRM), which includes all available timepoints (baseline, 3 months, and 6 months). This model accounts for within-subject correlation by specifying an unstructured covariance matrix.

Results will be presented as adjusted mean differences between groups with 95% confidence intervals and corresponding two-sided p-values. Least-squares means (LSMEANS) will be used to report group means adjusted for covariates.

The Intention-to-Treat (ITT) population will be the primary analytic set, including all randomized participants according to their allocated group. A Per-Protocol (PP) population, defined as participants with at least 70% adherence to the intervention, will be analyzed as a sensitivity approach.

Handling of Missing Data; for ANCOVA, missing data at 6 months will be addressed using multiple imputation under the missing-at-random (MAR) assumption. In MMRM, missing data are implicitly handled under MAR. Additional sensitivity analyses will explore the robustness of results to different missing-data mechanisms.

For ANCOVA, residuals will be checked for normality and homoscedasticity. If these assumptions are substantially violated, transformations or nonparametric methods will be considered. For MMRM, model fit will be evaluated and alternative covariance structures tested.

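### Section 9.3 confines ITT to participants with data at baseline, 6 and 18 months, while section 9.4.2 defines ITT as everyone randomised; per-protocol also has two incompatible definitions

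*Protocol*

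**What the plan says.** **ITT.** Section 9.3 describes the ITT set as "All randomized participants who have completed the minimum required follow-up and for whom clinical data and questionnaires are available at baseline (T0"), and then adds the 6-month and 18-month time points to the data that must be present. Section 9.4.2 states: "The Intention-to-Treat (ITT) population will be the primary analytic set, including all randomized participants according to their allocated group". It adds that, for the ANCOVA, "missing data at 6 months will be addressed using multiple imputation" under a missing-at-random assumption. On timing, section 9.1 says of the primary endpoint: "An efficacy analysis is planned and will be evaluated right after the end of the intervention".

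**Per-protocol.** Section 9.3 takes "Participants who have completed at least the main intervention session" who also have at least baseline and 6-month data. Section 9.4.2 has the set "defined as participants with at least 70% adherence to the intervention", and section 9.4.3 uses the same 70% threshold. Section 6.4 gives the adherence rule: "A participant will be considered adherent to the intervention if they complete the initial session and at least 70% of the follow-up sessions". Of the controls, section 4.1 says: "They will participate in periodic assessments but will not receive any components of the intervention program".

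**Time labels.** Section 9.3 describes T-6 and T-18 as 6 and 18 months after the intervention. The schedule table in section 8.1 places T-6 at the end of the intervention and T-18 twelve months after it.

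**The concern.** The primary analysis population is stated twice, with different members. This is not detail left for a later analysis plan, because the protocol gives two answers and does not rank them.

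If 9.3 were followed, inclusion in the 6-month primary analysis would depend on attendance and questionnaires a year later, which are events after randomisation. The trial is open-label. The study team may discontinue participants for not complying with the intervention (7.1), and those who cannot be contacted are excluded from it (7.3). Retention could therefore differ between arms and be related to outcome, and the comparison would lose the protection of randomisation. With both definitions in the protocol, two results could each be called ITT after the outcomes are known.

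**Working it through.** **1. Who is in which set**

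| Participant | ITT by 9.3 | ITT by 9.4.2 | PP by 9.3 | PP by 9.4.2 |
|---|---|---|---|---|
| Randomised, lost before month 6 | no | yes | no | depends on adherence only |
| Intervention arm, main session, 6-month data, no 18-month data | no | yes | yes | depends on adherence only |
| Intervention arm, complete data, under 70% adherence | yes | yes | yes | no |
| Intervention arm, at least 70% adherence, no 6-month data | no | yes | no | yes |
| Control, complete data | yes | yes | no (no session) | no (no sessions to adhere to) |

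- Rows 1 and 2 show that the two ITT sets differ. The 9.3 set requires 6-month data, so the imputation in 9.4.2 would have essentially nothing to impute.
- Row 2 shows that the 9.3 per-protocol set is not contained in the 9.3 ITT set, because it asks for less data.
- Rows 3 and 4 show that neither per-protocol set contains the other.
- Row 5 shows that, read literally, no between-arm per-protocol comparison exists.
- Membership of the 9.3 ITT set needs 18-month data, so it cannot be known at the end of the 6-month intervention, when 9.1 places the analysis.

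**2. Size, on the remission outcome**

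Inputs from 9.2: 60 per arm, two-sided alpha 0.05, control remission up to 5% (5% used), intervention remission at least 25% (25% used), 15% loss. Section 9.2 does not say when that loss occurs. Only loss after a known 6-month result is attributable to 9.3, so two cases are shown.

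Power uses the pooled-variance normal formula, with p̄ = (0.05 + 0.25)/2 = 0.15:

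power = Φ{ [0.20√n − 1.96√(2·0.15·0.85)] / √(0.05·0.95 + 0.25·0.75) }

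For n = 51: (1.428 − 0.990)/0.485 = 0.905, so power = 81.7%. By the same formula:

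| n per arm | 60 | 52 | 51 | 49 | 48 | 46 |
|---|---|---|---|---|---|---|
| power | 87.6% | 82.5% | 81.7% | 80.1% | 79.3% | 77.5% |

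The protocol's 52 per arm gives 82.5%, consistent with its stated beta below 0.2.

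*Case A: the 15% is lost by month 6.* That leaves 60 × 0.85 = 51 per arm. If 9.3 then removes an assumed 5% or 10% of these for missing month 18, 51 × 0.95 = 48.5 (taken as 48) or 51 × 0.90 = 45.9 (taken as 46) remain. Power is 79.3% or 77.5%.

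*Case B: all 15% is lost after month 6.* Then 0.15 × 60 = 9 known results per arm, 18 in total, are discarded. Power falls from 87.6% to 81.7%.

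These power figures assume that loss is unrelated to remission.

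**3. Bias, a separate scenario in which loss is related to remission**

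If a share d is dropped and remitters are dropped at d/2, the observed rate is p′ = p(1 − d/2)/(1 − d). Both arms are treated alike.

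| d | intervention | control | difference (true 20.0 points) |
|---|---|---|---|
| 5% | 25.7% | 5.1% | 20.5 |
| 10% | 26.4% | 5.3% | 21.1 |
| 15% | 27.2% | 5.4% | 21.8 |

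At the extreme, where only non-remitters in the intervention arm are dropped and d = 15%, 0.25/0.85 = 29.4% and the difference is 29.4 − 5.0 = 24.4 points.

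**The case against.** The strongest reply is that only 9.3 is out of line. Section 9.4.2, which is specific to the primary analysis, fixes the all-randomised set. Section 9.4.3 repeats the ITT principle, the missing-at-random handling and the 70% threshold, and carries the same missing-data approach to the other endpoints. Read that way, the harm never arises. This weighs in favour of 9.4.2 as the intended rule, but 9.3 is the section that defines the populations and nothing subordinates it, so the correction is still needed.

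On size, several points stand:

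- The figures concern remission. The analysis in 9.4.2 is an ANCOVA of HbA1c change, whose power cannot be computed because no standard deviation or effect size is given.
- Power falls below 80% only in Case A, which adds a loss the protocol does not state.
- Power loss and bias do not add up. With the half-rate proportions in section 3 of the working, power is 80.6% (n = 48), 80.2% (n = 46) and 85.6% (n = 51).
- Half-rate bias is only 0.5 to 1.8 points, and 24.4 is an extreme.

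On per-protocol, one would naturally apply adherence to the intervention arm only, and the analysis is only a sensitivity analysis. That softens the point about controls but does not reconcile the two definitions. The time labels are a slip, since the T-6 and T-18 tags are defined in 8.1.

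**Conclusion.** The concern holds and must be fixed. The protocol gives two incompatible definitions of its primary analysis set and two of its per-protocol set, and does not say which governs. That conclusion rests on the text alone.

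The numerical effect arises only if 9.3 governs, and it depends on when loss occurs and whether it relates to remission. Under the stated assumptions the power loss is modest (87.6% to 81.7% in Case B; 81.7% to 79.3% or 77.5% in Case A). The difference is inflated by 0.5 to 1.8 points at the half rate, or 4.4 points at the extreme. The more serious consequences are a primary comparison selected on 18-month retention, and a primary set left open until after outcomes are seen.

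**What to change.** - **ITT.** In 9.3, define ITT as all randomised participants analysed in their allocated arm, regardless of follow-up or adherence. This includes any allocated participant who never starts and is replaced under 7.2.
- **Data requirement.** Remove the 18-month requirement from every 6-month analysis.
- **Missing outcomes.** Handle missing 6-month outcomes by multiple imputation as in 9.4.2. That text is written for the HbA1c ANCOVA, so extend it to 6-month remission, together with the sensitivity analyses for other missing-data mechanisms that 9.4.2 already plans.
- **Per-protocol.** Define it once and use it in 9.3, 9.4.2 and 9.4.3: intervention participants who meet the 70% rule of 6.4, plus controls with 6-month data. Keep it as a sensitivity analysis, and state that it compares a group selected on adherence with controls who are not.
- **Labels.** Align the time-point wording in 9.3 with the 8.1 schedule (end of intervention, and 12 months after it). Section 10.1.4 repeats the same wording and should be aligned too.

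The cost is protocol wording only, with no added visits or data. The reported remission rate may be slightly lower than in a completers set.
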